16.1.2. MISSING DATA METHODS FOR PRIMARY EFFICACY VARIABLE

Patients with a missing DRC-adjudicated overall response at Day 42 will be considered as failures.

Note: All mITT patients will be counted in the denominator of the %/ rate calculation at every visit through Day 84,

Document:	\\weedc-vnasc01\BIOSdata\F2G\F901318\		
Author:		Version Number:	3.0
		Version Date:	06Apr2023
Template No.:	CS_TP_BS016 Revision 6	Reference:	CS_WI_BS005
Effective Date:	02Dec2019		

even if they discontinue early.

16.1.3. PRIMARY ANALYSIS OF PRIMARY EFFICACY VARIABLE

The primary objective of this study is to describe the DRC-adjudicated efficacy of F901318 as treatment for infections due to resistant fungi in patients lacking suitable alternative treatment options. More specifically, the primary efficacy analysis will focus on the DRC-adjudicated efficacy in terms of DRC-adjudicated overall response at Day 42.

The primary efficacy analysis will be performed for the mITT population.

Based on the DRC-adjudicated overall response categorized as success or failure (as defined above in [Section 16.1.1](#)), a response rate will be calculated for the proportion of successes. A 95% exact Clopper-Pearson CI for the single binomial proportion ([Clopper & Pearson, 1934](#)) will be calculated. An analysis comparing the 95% CI for the overall response rate with an estimated historical response rate (and 95% CI) will be presented in a separate report outside of the CSR. Corresponding estimated historical response rates in relevant control populations will be assessed using analyses of available clinical databases, and presented in a similar manner as the calculated F901318/0032 study response rate, outside of the CSR.

In addition, all DRC-adjudicated data will be summarised descriptively and listed.

Document: \\weedc-vnasc01\BIOSdata\F2G\F901318 [REDACTED]
Author: [REDACTED] Version Number: 3.0
Version Date: 06Apr2023
Template No.: CS_TP_BS016 Revision 6 Reference: CS_WI_BS005
Effective Date: 02Dec2019

16.1.4. SENSITIVITY ANALYSIS OF PRIMARY EFFICACY VARIABLE

The primary efficacy analysis will be repeated for the PPAS.

Additionally, a sensitivity analysis of modified overall response will be performed for the mITT population where success will be defined as follows:

Modified Overall Response	Criteria
Success :	
• Clinical: Meets Criteria for Resolution-Complete or Resolution-Partial;• Radiological (if assessed): Shows no change or improvement of radiological abnormalities ($\geq 0\%$ response);• Mycological: Meets criteria for presumed or documented eradication.

The only required data are the clinical and mycological data. The absence of radiological evaluations at a given time point does not prevent assignment to Modified Overall Response as Success.

Similar to the primary analysis, a response rate will be calculated for the proportion of successes. A 95% exact Clopper-Pearson CI for the single binomial proportion will be calculated.

16.1.5. SECONDARY EFFICACY VARIABLES & DERIVATIONS

16.1.5.1. DRC-adjudicated overall response at Day 7, Day 14, Day 28, main study phase EOT, Day 84, and 4-week follow-up

The text on the description and derivations as set out for the primary efficacy variable applies for this secondary efficacy variable.

For the 4-week follow-up visit, only patients who did not enrol in the extension treatment phase will be considered.

16.1.5.2. Investigator-assessed overall response at Day 7, Day 14, Day 28, Day 42, main study phase EOT, Day 84, and 4-week follow-up

A secondary efficacy variable is the Investigator-assessed overall response at Day 7, Day 14, Day 28, Day 42, main study phase EOT, Day 84, and 4-week follow-up, as determined by the Investigator using all available assessment results including clinical, mycological and radiological results.

Document: \\weedc-vnasc01\BIOSdata\F2G\F901318\ [Redacted]
Author: [Redacted] Version Number: 3.0
Version Date: 06Apr2023
Template No.: CS_TP_BS016 Revision 6 Reference: CS_WI_BS005
Effective Date: 02Dec2019

Investigator-assessed overall response is collected on the Investigator's diagnostic and response assessment eCRF page.

Refer to [Table A](#) for the criteria for invasive fungal disease assessment of overall response. Number and % of patients will be summarised for these categories.

N and % will also be summarised for the 3 categories of Success (Success-Complete, Success-Partial), Stable disease (Failure-Stable) and Failure (Failure-Progression, Death, and those patients for whom data at Day 42 cannot be collected or who are considered not evaluable at Day 42).

For statistical analysis of response rate, values will be assigned to the Investigator-assessed overall response as follows:

- Success (Success-Complete, Success-Partial),
- Failure (Failure-Stable, Failure-Progression, Death, and those patients for whom data at the specific visit cannot be collected or who are considered not evaluable at the specific visit).

Patients withdrawn from study medication due to an unsuccessful overall outcome are required per protocol to return for the main study phase EOT visit but will not be asked to return for the Day 42 and/or Day 84 visits; these patients will be considered as failures at all subsequent timepoints.

Similarly to the primary endpoint, a important analysis will be performed in which a stable disease outcome will be considered a success, i.e. assigning the Investigator response to categories as follows;

- Success (Success-Complete, Success-Partial, Failure-Stable)
- Failure (Failure-Progression, Death, and missing/not evaluable).

For the 4-week follow-up visit, only patients who did not enrol in the extension treatment phase will be considered.

16.1.5.3. DRC-adjudicated and Investigator-assessed clinical response at Day 7, Day 14, Day 28, Day 42, main study phase EOT, Day 84, and 4-week follow-up

Other secondary efficacy variables include the DRC-adjudicated and Investigator-assessed clinical response at Day 7, Day 14, Day 28, Day 42, main study phase EOT, Day 84, and 4-week follow-up.

DRC-adjudicated clinical response is determined by an independent DRC and collected in a separate DRC adjudicated outcome database.

Document:	\\weedc-vnasc01\BIOSdata\F2G\F901318\		
Author:		Version Number:	3.0
		Version Date:	06Apr2023
Template No.:	CS_TP_BS016 Revision 6	Reference:	CS_WI_BS005
Effective Date:	02Dec2019		

Investigator-assessed clinical response is collected on the Investigator’s diagnostic and response assessment eCRF page.

Table B presents the criteria for clinical response.

Table B: Criteria for clinical response

Clinical Response	Criteria
Resolution-Complete	
For patients with attributable clinical symptoms and physical findings of IFD present at baseline, Resolution-Complete is assigned if:
 
 a. there is resolution of all attributable clinical symptoms and physical findings of IFD present at baseline or that appeared at a subsequent prior visit 
AND
 
 b. no new clinical symptoms and physical findings of IFD are noted at the current visit. 
For patients lacking attributable clinical symptoms and physical findings of IFD present at baseline*, Resolution-Complete is assigned if
 
 a. there is resolution of all attributable clinical symptoms and physical findings that appeared at a subsequent prior post-baseline visit 
AND
 
 b. no new clinical symptoms and physical findings of IFD are noted at the current visit. 
AND
 
 c. patient meets mycological criteria for Eradication or Presumed Eradication
Resolution-Partial	
For patients with attributable clinical symptoms and physical findings of IFD present at baseline, Resolution-Partial is assigned if
 
 a. there is some persistence of the attributable clinical symptoms and physical findings of IFD noted either at baseline or at a subsequent prior post-baseline visit but there is improvement in at least some of these same symptoms and findings 
AND
 
 b. no worsening of any of these same symptoms and findings 
AND
 
 c. no new clinical symptoms and physical findings of IFD at the current visit. 
For patients lacking attributable clinical symptoms and physical findings of IFD present at baseline*, Resolution-Partial is assigned if

Document: \\weedc-vnasc01\BIOSdata\F2G\F901318\ [Redacted]
 Author: [Redacted] Version Number: 3.0
 Version Date: 06Apr2023
 Template No.: CS_TP_BS016 Revision 6 Reference: CS_WI_BS005
 Effective Date: 02Dec2019

F2G Ltd.
 PROTOCOL F901318/0032

	a. there is some persistence of the attributable clinical symptoms and physical findings of IFD noted at a subsequent prior post-baseline visit but there is improvement in at least some of these same symptoms and findings AND b. no worsening of any of these same symptoms and findings AND c. no new clinical symptoms and physical findings of IFD at the current visit. AND d. patient meets mycological criteria for Eradication or Presumed Eradication.
Failure-Stable	Neither worsening nor improvement in any attributable clinical symptoms and physical findings present at baseline or that appeared at a subsequent prior visit AND no new clinical symptoms and physical findings of IFD at the current visit.
Failure-Progression	Shows EITHER worsening in one or more attributable clinical symptoms and physical findings present either at baseline or that appeared at a subsequent prior visit OR appearance of new clinical symptoms and physical findings of IFD at the current visit.
Results not available/patient unevaluable	Visit and/or assessment of clinical symptoms and physical findings of IFD was not performed

Note: If the qualifying infection was diagnosed before baseline, data regarding the prior symptoms and prior evaluation(s) of the invasive fungal infection may need to be considered.

Note: That the rules defining success are tested in sequence beginning with Success-Complete.

For statistical analysis of clinical response rate, values will be assigned to the DRC-adjudicated and Investigator-assessed clinical response as follows:

- Success (Resolution-Complete, Resolution-Partial),
- Failure (Failure-Stable, Failure-Progression, Deaths, and those patients for whom data at the specific visit cannot be collected or who are considered not evaluable at the specific visit).

Similarly to primary analysis, patients with a stable disease outcome will be considered a success, i.e. assigning the DRC adjudicated response to categories as follows.

- Success (Resolution-Complete, Resolution-Partial, Failure-Stable)
- Failure (Failure-Progression, Death, and those patients for whom data at the specific visit cannot be collected)

Document: \\weedc-vnasc01\BIOSdata\F2G\F901318\ [Redacted]
 Author: [Redacted] Version Number: 3.0
 Version Date: 06Apr2023
 Template No.: CS_TP_BS016 Revision 6 Reference: CS_WI_BS005
 Effective Date: 02Dec2019

or who are considered not evaluable at the specific visit)

Patients withdrawn from study medication due to an unsuccessful overall outcome are required per protocol to return for the main study phase EOT visit but will not be asked to return for the Day 42 and/or Day 84 visits; these patients will be considered as failures at all subsequent timepoints.

For the 4-week follow-up visit, only patients who did not enrol in the extension treatment phase will be considered.

16.1.5.4. DRC-adjudicated and Investigator-assessed radiological response at Day 7, Day 14, Day 28, Day 42, main study phase EOT, Day 84, and 4-week follow-up

DRC-adjudicated and Investigator-assessed radiological response at Day 7, Day 14, Day 28, Day 42, main study phase EOT, Day 84, and 4-week follow-up are secondary efficacy variables.

DRC-adjudicated radiological response is determined by an independent DRC and collected in a separate DRC adjudicated outcome database.

Investigator-assessed radiological response is collected on the Investigator's diagnostic and response assessment eCRF page.

For the 4-week follow-up visit, only patients who did not enrol in the extension treatment phase will be considered.

Table C presents the criteria for radiological response.

Table C: Criteria for radiological response

Radiology Response
≥ 90% improvement in aggregate (across all lesions if more than one lesion)
≥ 50 to < 90% improvement in aggregate (across all lesions if more than one lesion)
≥ 25% to < 50% improvement in aggregate (across all lesions if more than one lesion)
No change 0%* to < 25 % improvement in aggregate (across all lesions if more than one lesion)
Worsening in aggregate (across all lesions if more than one lesion)
No signs on radiological images at screening
Results not available (i.e. visit and/or radiological assessment was not performed at the scheduled timepoint (Day 7, Day 14, Day 28, Day 42, EOT, Day 84 or 4-week FU)).

Radiological response will also be presented grouped in categories and presented at output level:

Document: \\weedc-vnasc01\BIOSdata\F2G\F901318\ [Redacted]
Author: [Redacted] Version Number: 3.0
Version Date: 06Apr2023
Template No.: CS_TP_BS016 Revision 6 Reference: CS_WI_BS005
Effective Date: 02Dec2019

F2G Ltd.
PROTOCOL F901318/0032

- “Success” if response is $\geq 90\%$ improvement in aggregate (across all lesions if more than one lesion)
- “Improvement” if response is ≥ 50 to $< 90\%$ improvement in aggregate (across all lesions if more than one lesion) and $\geq 25\%$ to $< 50\%$ improvement in aggregate (across all lesions if more than one lesion)
- “Stable” if response is No change 0%* to $< 25\%$ improvement in aggregate (across all lesions if more than one lesion)
- “Worsening” if response is Worsening* in aggregate (across all lesions if more than one lesion)
- “Death” if death
- “Not Evaluable/Missing” if response is (No signs on radiological images at screening, Results not available, Missing)

16.1.5.5. DRC-adjudicated and Investigator-assessed mycological response at Day 7, Day 14, Day 28, Day 42, main study phase EOT, Day 84, and 4-week follow-up

DRC-adjudicated and Investigator-assessed mycological response at Day 7, Day 14, Day 28, Day 42, main study phase EOT, Day 84, and 4-week follow-up are also secondary efficacy variables.

DRC-adjudicated mycological response is determined by an independent DRC and collected in a separate DRC adjudicated outcome database.

Investigator-assessed mycological response is collected on the Investigator’s diagnostic and response assessment eCRF page.

Table D presents the criteria for mycological response.

Table D: Criteria for mycological response

Mycological Response	Criteria
Eradication	Eradication of the original causative organism cultured or identified by histology/cytology at baseline and no emergence of new causative organisms at that visit.
Presumed Eradication	Missing documentation of the eradication of the original causative organism cultured or identified by histology/cytology at baseline and no documentation of emergence of new causative organisms at that visit plus resolution of all or some attributable clinical symptoms and physical findings of IFD present at baseline and/or of those that appeared at a subsequent visit and no appearance of new attributable clinical symptoms and physical findings of IFD at that visit.

Document: \\weedc-vnasc01\BIOSdata\F2G\F901318\ [Redacted]
Author: [Redacted] Version Number: 3.0
Version Date: 06Apr2023
Template No.: CS_TP_BS016 Revision 6 Reference: CS_WI_BS005
Effective Date: 02Dec2019

F2G Ltd.
PROTOCOL F901318/0032

Persistence	Persistence of the original causative organism cultured or identified by histology /cytology at baseline or emergence of a new causative organism at that visit
Presumed Persistence	Missing documentation of the persistence of the original causative organism cultured or identified by histology/cytology at baseline and no documentation of emergence of new causative organisms at that visit plus either (i) no resolution or (ii) worsening of any attributable clinical symptoms and physical findings of IFD present at baseline and/or of those that appeared at a subsequent visit and/or appearance of new attributable clinical signs and physical findings of IFD at that visit.
No Mycological Follow-up Results Available	For whatever reason no diagnostic test done at the scheduled timepoint AND other data are insufficient to support assigning Presumed Eradication or Presumed Persistence).
No Mycological Evidence at Baseline	Negative diagnostic test(s) results at baseline, or not done at baseline.
Recurrent	Re-appearance of same species after apparent negative culture PLUS additional antifungal treatment becomes necessary.
Emergent	Appearance of new species after apparent negative culture PLUS additional antifungal treatment becomes necessary. New species emerging during the first 7 days of therapy with F901318 are presumed to have been present at baseline and are classified as Baseline secondary infections rather than Emergent infections.

Patients with a mycological evaluation of “No Mycological Follow-up Results Available” and “Not Done” at a specific visit will be assigned an outcome of:

- “Presumed Eradication” if they are a clinical success at the specific visit,
- “Presumed Persistence” if they are deemed a clinical failure, or if the clinical response is missing at the specific visit.
- Patients with missing clinical response are assigned a response of “No mycological or clinical follow-up available”.

For statistical analysis of mycological response, values will be assigned to the DRC-adjudicated and Investigator-assessed mycological response as follows:

- Success (Eradication, Presumed Eradication),
- Failure (Persistence, Presumed Persistence, Recurrent/Emergent infections, death or any other response except Eradication or Presumed Eradication).

Patients withdrawn from study medication due to an unsuccessful overall outcome are required per protocol to return

Document: \\weedc-vnasc01\BIOSdata\F2G\F901318 [Redacted]
 Author: [Redacted] Version Number: 3.0
 Version Date: 06Apr2023
 Template No.: CS_TP_BS016 Revision 6 Reference: CS_WI_BS005
 Effective Date: 02Dec2019

F2G Ltd.
PROTOCOL F901318/0032

for the main study phase EOT visit but will not be asked to return for the Day 42 and/or Day 84 visits; these patients will be considered as failures at all subsequent timepoints.

For the 4-week follow-up visit, only patients who did not enrol in the extension treatment phase will be considered.

16.1.5.6. All-cause mortality rate at Day 42, main study phase EOT, Day 84, and 4-week follow-up

All-cause mortality rate at Day 42, main study phase EOT, Day 84, and 4-week follow-up is a secondary efficacy variable.

Survival status is captured on the Survival Status eCRF page.

Mortality rate at visit X is calculated as:

$$\frac{\text{Number of deaths up to and including visit X}}{\text{mITT population}}$$

For the 4-week follow-up visit, only patients who did not enrol in the extension treatment phase will be considered.

16.1.5.7. Patient-reported outcome at Day 42 and Day 84

[figure not shown]
A secondary efficacy variable is the quality of life (patient-reported outcome) [redacted] based on the EQ-5D-5L questionnaire. Patient-reported outcome is collected on the Health Questionnaire eCRF page.

The EQ-5D-5L health questionnaire is an assessment where the following five qualitative items are evaluated, i.e. does the patient have issues with:

- Mobility
- Personal care
- Usual activities
- Pain/Discomfort
- Anxiety/Depression

Document: \\weedc-vnasc01\BIOSdata\F2G\F901318 [redacted]
Author: [redacted] Version Number: 3.0
Version Date: 06Apr2023
Template No.: CS_TP_BS016 Revision 6 Reference: CS_WI_BS005
Effective Date: 02Dec2019

Answers to the five qualitative items include:

- None
- Slight
- Moderate
- Severe
- Extreme

The EQ-5D-5L health questionnaire also includes the quantitative item:

- Visual analogue scale (VAS) score, where the scale is numbered from 0 to 100. 100 means the best health the patient can imagine. 0 means the worst health the patient can imagine.

The EQ-5D-5L profile will be converted into a weighted health state utility value, the EQ-5D-5L Index, by applying a US-based value set derived from a standardized protocol developed by the EuroQol Group (Pickard et al). For derivation for EQ-5D-5L index score, please refer [Appendix 3 \(Reference⁴\)](#). The parameter estimate values are presented in [table 2](#). The parameter estimate for each questionnaire response is presented. i.e. Mobility Slight (MO2)= 0.096.

Please note that score for level 1 of each questionnaire item is 0. i.e. MO1=0, SC1=0, UA1=0, PD1=0 & AD1=0.

The overall health index score(HIS) for a patient at visit is derived by subtracting all the estimate values from 1, ie.HIS = 1 - (MO_i + SC_i + UA_i + PD_i + AD_i), where i=1,2,3,4,5 response score to respective questionnaire.

- If HIS=1 means perfect health.
 - HIS <1 means there is some negative impairment.

Please note that HIS cannot be >1.

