If relevant mycology findings occur after successful mycological response (proven or presumed eradication), an evaluation will be made as to whether the infection is recurrent (same species as at baseline) or emergent (different species compared with baseline). Patients with recurrent or

emergent infection will be classified as mycological failure from the visit onwards where positive cultures were reported.

Recurrent – Re-appearance of same species after apparent negative culture PLUS additional antifungal treatment becomes necessary.

Emergent – Appearance of new species after apparent negative culture PLUS additional antifungal treatment becomes necessary. New species emerging during the first 7 days of therapy with F901318 are presumed to have been present at baseline and are classified as Baseline secondary infections rather than Emergent infections.

6.3.1.5 *Investigator’s Assessment of Overall Response*

The Investigator’s assessment of overall response will be based on all available assessments (clinical, radiological and mycological) as described in Sections 6.3.1.1, 6.3.1.2 and 6.3.1.4. It is essential that the same methods and assessments are used to define the IFD diagnosis at baseline and to evaluate the response to treatment.

Treatment “success” is defined as **complete** or **partial**.

Treatment “failure” is defined as **stable** response or **progression** of IFD.

Of the three components of overall response, only clinical and mycological responses are required. Patients who lack data at a visit (e.g., the visit data were not collected for some reason) or who are not evaluable at the visit because these data cannot be collected are considered failures.

The criteria for assessment of overall response are summarised in Table 5:

Table 5 Criteria for Assessment of Overall Response

Success - complete*:
	
 • Clinical: Meets criteria for Resolution-Complete; AND • Radiological (if assessed): Shows resolution of radiological abnormalities ($\geq 90\%$ response); AND • Mycological: Meets criteria for presumed or documented eradication.

Success - partial*:
	
 • Clinical: Meets criteria for Resolution-Complete or Resolution-Partial; AND • Radiological (if assessed): Shows resolution or improvement of radiological abnormalities (at least 25% response); AND • Mycological: Meets criteria for presumed or documented eradication.

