8.2.3 Secondary Efficacy Endpoints

- **DRC-adjudicated overall response (overall and by DRC-adjudicated disease category) at Day 7, Day 14, Day 28, main study phase EOT, Day 84 and 4-week FU* (as determined by an independent DRC using a combination of clinical, mycological and radiological results) categorised as:**
 - **Success**
 - **Failure**
- **Investigator-assessed overall response (overall and by DRC-adjudicated disease category as determined by Investigator using all available assessment results including clinical, mycological and radiologic results) at Day 7, Day 14, Day 28, Day 42, main study phase EOT, Day 84 and 4-week FU* will be categorized as:**
 - **Success**
 - **Failure (where failure includes those patients with missing clinical responses or considered not evaluable)**
- **DRC-adjudicated and Investigator-assessed clinical response overall and by DRC-adjudicated disease category at Day 7, Day 14, Day 28, Day 42, main study phase EOT, Day 84 and 4-week FU* will be categorised as:**
 - **Success (categories of Resolution-Complete and Resolution-Partial)**
 - **Failure (categories of Failure-Stable, Failure-Progression, and Results not available)**
- Where appropriate for the IFD, **DRC-adjudicated and Investigator-assessed radiological response** at Day 7, Day 14, Day 28, Day 42, main study phase EOT, Day 84 and 4-week FU*. will be presented overall, by the 5 DRC-adjudicated disease categories and in addition by baseline susceptibility category.
- **DRC-adjudicated and Investigator-assessed mycological response** at Day 7, Day 14, Day

28, Day 42, main study phase EOT, Day 84 and 4-week FU* will be presented overall, by the five DRC-adjudicated disease categories and in addition by baseline susceptibility category based on the categorised response of:

- **Success (Proven or presumed eradication)**
- **Failure (Persistence, presumed persistence, Recurrent or emergent infection or any other response except proven or presumed eradication)**

- **All-cause mortality** rate will be summarised overall and by each of the five DRC-adjudicated disease categories at Day 42, main study phase EOT, Day 84 and 4-week FU*. In addition, overall survival (median time to death) will be presented.

Patients with complete clinical response to study drug treatment will also be evaluated for relapse of the treated IFD and for newly emergent IFD at selected study visits up to the main study phase EOT visit (Day 84 to Day 90).

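### The SAP omits the protocol's rule that a recurrent or emergent infection remains a mycological failure, so some relapsed patients can be scored as mycological successes at later visits

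*SAP*

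**What the plan says.** **Protocol.** Section 6.3.1.4, under mycological response after initial success, says that patients with recurrent or "emergent infection will be classified as mycological failure from the visit onwards where positive cultures were reported". It makes no exception for later clearance. The endpoint definition in Section 8.2.3 gives the categories only: "Failure (Persistence, presumed persistence, Recurrent or emergent infection or any other response except proven or presumed eradication".

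**SAP.** Table D in 16.1.5.5 takes over the protocol's definitions of the two categories. Recurrent, for example, is "Re-appearance of same species after apparent negative culture PLUS additional antifungal treatment becomes necessary". The sentence that fixes such patients as failures from then on is not carried over. The analysis rule lists as failure "Failure (Persistence, Presumed Persistence, Recurrent/Emergent infections, death or any other response except Eradication or Presumed Eradication".

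Two SAP rules lead to success, and both look only at the current visit:
- Eradication is "Eradication of the original causative organism cultured or identified by histology/cytology at baseline and no emergence of new causative organisms at that visit".
- When mycological follow-up is not available or not done, the patient becomes Presumed Eradication "if they are a clinical success at the specific visit".

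The section has one carry-forward. It opens "Patients withdrawn from study medication due to an unsuccessful overall outcome are required per protocol to return" for the end-of-treatment visit but not for Day 42 or Day 84, and ends "these patients will be considered as failures at all subsequent timepoints".

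**The concern.** The protocol makes failure after relapse permanent. The SAP's rules, applied as written to each visit's record, do not. A patient who was Recurrent at one visit and is culture-negative at the next meets Eradication. A patient who was Recurrent and is not retested, but has improved clinically, is imputed Presumed Eradication. Both are failures under protocol 6.3.1.4 and successes under the SAP.

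By definition these patients needed additional antifungal treatment, so they are not the patients a reader of the protocol expects to find among the later successes. The later mycological response rates would be too high by the protocol's own standard, and nothing legible in SAP 3.3 would alert the reader. The mycological component also feeds overall response, because Success in SAP Table A requires presumed or documented eradication.

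**Working it through.** There is no figure in the plan to reproduce, so the check sets the passages side by side and then works out the effect per patient.

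**1. Which relapsed patients does the SAP already keep as failures?** Table A makes a recurrent or emergent infection Failure-Progression, which is an unsuccessful overall outcome. If study drug is withdrawn for it, the carry-forward applies and the patient stays a failure. Protocol and SAP agree for this group.

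**2. Which relapsed patients fall outside the carry-forward?**
- (a) Patients who stopped treatment after a successful outcome. Protocol 5.1 requires those who finish before Day 42 to return at Day 42 and Day 84. A relapse after stopping is not a withdrawal from study drug.
- (b) Patients kept on F901318 with another antifungal added. Protocol 5.9.2.1 discourages this but permits it.

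**3. What happens to groups (a) and (b) at a later visit?**

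| Later-visit finding | Protocol 6.3.1.4 | SAP 16.1.5.5 as written |
|---|---|---|
| Organism eradicated, no new organism | Failure | Eradication: success |
| Mycology not done, clinical success | Failure | Presumed Eradication: success |
| Mycology not done, clinical failure | Failure | Presumed Persistence: failure |

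The second row matters because protocol 6.3.1.4 schedules the investigator's mycological assessment only at Day 7, Day 42, Day 84/end of treatment and 4 weeks after. At other visits it is done as clinically indicated, so untested visits are foreseeable.

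**4. Effect per patient.** SAP 16.1.6.1 sets the mycology denominator N as all patients with mycological evidence at baseline. The value of N is not given. If k patients are relapsed-then-success at a visit, the SAP rate exceeds the protocol rate by k/N. For k = 1 that is 1/100 = 1 point, or 1/200 = 0.5 point.

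**5. Illustration.** Assumptions: a 50% success rate under the SAP's visit-specific rules, and k equal to 2%, 5% or 10% of N. Intervals are the SAP's exact Clopper-Pearson 95% limits: lower = Beta quantile 0.025 with parameters (x, N−x+1), upper = Beta quantile 0.975 with parameters (x+1, N−x), where x is the number of successes.

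| N | k | x under the onward rule | Rate (95% CI) |
|---|---|---|---|
| 100 | 0 | 50 | 50.0% (39.8 to 60.2) |
| 100 | 2 | 48 | 48.0% (37.9 to 58.2) |
| 100 | 5 | 45 | 45.0% (35.0 to 55.3) |
| 100 | 10 | 40 | 40.0% (30.3 to 50.3) |
| 200 | 0 | 100 | 50.0% (42.9 to 57.1) |
| 200 | 4 | 96 | 48.0% (40.9 to 55.2) |
| 200 | 10 | 90 | 45.0% (38.0 to 52.2) |
| 200 | 20 | 80 | 40.0% (33.2 to 47.1) |

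Neither k nor the 50% comes from the documents. The table shows scale, not an estimate.

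**6. Overall response.** The footnote to Table A tests the Success rules before the Failure rules. If the mycological component has reset to Eradication and the clinical component qualifies, Success can be assigned before the clause on recurrent infection or alternative antifungal treatment is reached. That makes an effect on overall response possible. It does not show that one occurs.

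**The case against.** The strongest reply is that the SAP is silent rather than contrary. Its failure list is almost that of protocol 8.2.3, with death added, and 8.2.3 does not repeat the onward rule either. The imputation from clinical success is itself in protocol 8.8.2. The onward rule can be read as an instruction to the assessor. An investigator or DRC member who applies 6.3.1.4 would record failure from that visit on, and the SAP would count it as failure. DRC practice is set in its charter, which is not among these documents. Mycological response is also a secondary, descriptive endpoint.

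This stands in part. It means that a relapsed patient *can* return as a success, not that one will. It does not close the gap. Protocol 8.8.2 bases the secondary analyses on the Section 6.3 definitions, which include the onward rule. Protocol 8.2.1 leaves the full analysis details to the SAP. The imputation is also an analysis rule: it assigns success where no mycological follow-up was recorded, and neither document says that an earlier recurrence blocks it.

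The documents do not support four stronger readings that a reader might infer:
- **The SAP scores every visit in isolation.** It does not; the carry-forward for withdrawn patients follows directly after the failure list.
- **Clearance by another drug is credited to F901318.** The definition requires additional antifungal treatment, not a different agent. Protocol 5.1 allows patients who stopped after success to resume F901318 itself.
- **The Day 42 primary endpoint is overstated by a similar amount.** That would need eradication, relapse, no withdrawal for failure, and renewed clinical and mycological success, all by Day 42.
- **A bias can be computed from an assumed relapse rate in 200 patients.** The planned enrolment of 200 is not the mycology denominator, and some relapsed patients will be withdrawn and already kept as failures.

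**Conclusion.** The concern holds in limited form. The SAP leaves out a protocol classification rule, does not declare this in the legible part of Section 3.3 (some of which is redacted), and contains two visit-specific routes by which a patient the protocol fixes as a failure can be scored a success. The gap is confined to relapsed patients not withdrawn from study drug for an unsuccessful outcome, and to cases where the assessor has not already recorded failure under 6.3.1.4.

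The size is k/N for the later-visit mycological rates. Neither k nor N can be derived from the documents. An effect on investigator-assessed or DRC-adjudicated overall response is possible through the mycological component, but it cannot be quantified. The point is worth correcting before analysis because the remedy is small and the two documents should give the same answer for the same patient.

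**What to change.** In SAP 16.1.5.5 and 16.1.6.1, state that once Recurrent or Emergent is recorded, mycological response is failure at that visit and at all later visits. State also that this takes precedence over the imputation of Presumed Eradication from clinical success.

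In SAP 16.1.1 and 16.1.5.2, state that the mycological component of overall response follows the same rule. Confirm that the DRC charter applies it. DRC adjudications should be aligned through the charter, not overwritten by programming.

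If the sponsor intends visit-specific scoring instead, it should list that departure from protocol 6.3.1.4 in SAP 3.3 with a reason.

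The cost is a few sentences, one derivation rule for mycological response and a check of the charter. Later-visit rates may be slightly lower.
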